usually temporary and confined to the lower back. Headache may occur in about 5% of elderly adults who receive an LP using the ADCS LP protocol. Less commonly, in about 1-4% of subjects, a persistent low-pressure headache may develop, probably due to leakage of CSF. On rare occasions, a blood patch (injection of some of the subject's blood to patch the CSF leak) may be needed. Potential but rare risks of LP include infection, damage to nerves in the back, bleeding into the CSF space, and death. Risk for these events is less than 1%.

General. Blood collection may be associated with transient discomfort and bruising, and a small risk of infection. Cognitive testing may produce frustration in some subjects. Questionnaires about mood may uncover or potentiate feelings of dysthymia and helplessness.

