### 5.4 Efficacy Analysis

#### 5.4.1 Analysis of Primary Outcome

To address **Aim 1** for the primary efficacy analysis, longitudinal scores from baseline through the first 12 months will be analyzed using a mixed effects model for repeated measures (MMRM) to assess differences in scores between intervention groups. The MMRM model will include terms for time, intervention, and baseline ADAS-Cog-Exec, intervention-by-time

interaction, baseline ADAS-Cog-Exec by time interaction, plus covariates that include site, ApoE4 carrier status, sex, and additional covariates meeting the criteria below.

Time will be treated as categorical. An analysis of covariance model imputing missing data with multiple imputation will be used as a sensitivity analysis. As a second sensitivity analysis, a similar MMRM model will be fit with time modeled as a continuous factor. If the longitudinal patterns over time are markedly non-linear, such as might occur due to learning effects, a quadratic term for time will be included in the model. In this case the intervention-by-time linear term assesses whether there is a relative difference between intervention groups that grows linearly with time. Potential confounders (baseline Walk Test time, age, education, 3MSE baseline score, and use of cholinesterase inhibitors) will be included in efficacy analyses as covariates if the following two conditions are satisfied: (1) imbalance at baseline ( $p < 0.1$ ) and, (2) association between the covariate and the response ( $p < 0.15$ ). Safety data will be analyzed using exact contingency table methods by intervention group assignment.

Differences in the primary outcome of change in ADAS-Cog-Exec between intervention groups will be tested at the two-sided 5% significance level. No adjustment to the type 1 error level will be made for secondary analyses.

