#### 5.4.2 Analyses of Secondary Outcomes

**Aims 2–4:** Similar analyses to that described for the primary analysis will be performed on the Clinical Dementia Rating Scale – Sum of Boxes (CDR-SB), ADAS-Cog13 total score, Executive Function and Episodic Memory Composites, tests of daily living skills (ADCS–Activities Of Daily Living–MCI [ADCS-ADL-MCI], Behavior Rating Inventory Of Executive Function–Adult Version [BRIEF-A]), mood and health-related quality of life (Neuropsychiatric Inventory [NPI], 36-Item Short-Form Health Survey [SF-36]), EuroQol 5-Item Health Questionnaire [EQ5D]), and subjective memory concerns (Cognitive Change Index).

**Aim 5:** Change in brain volume and inter-regional correlations in brain functional activity will be compared between treatment groups. The analysis will be completed separately for each volumetric and functional MRI parameter.

**Aim 6:** CSF biomarkers of brain health and disease will be examined using a similar analytic strategy to that described for the analysis of the primary outcome using MMRM and other sensitivity models to test for intervention effects. Covariate adjustment, sensitivity analyses, and multiple imputation analyses will be carried out as specified under Aim 1.

**Aim 7:** To examine whether sociodemographic factors, genotype, actigraphy outcomes, or baseline cognitive and biomarker profiles predict treatment response, MMRM and sensitivity models as described above will be performed using subgroup analyses. Model fitting and covariate adjustment will be carried out as specified under Aim 1.

**Aim 8:** To examine the enduring cognitive and behavioral effects of the intervention following the 6-month unsupervised exercise extension, MMRM and sensitivity models as described above will be performed. Model fitting and covariate adjustment will be carried out as specified under Aim 1.

**Aim 9:** To examine the impacts of the intervention on the study partner, MMRM and sensitivity models as described above will be performed on data obtained using the Study Partner Self-Assessment Questionnaire.

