## 9.5 Month 12 (Visit 4) / or Early Termination

The Month 12 assessment will provide the primary endpoints to evaluate trial efficacy, and should be completed 12 months (+/- 2 weeks) from the participant's first appointment at the YMCA that initiated the intervention. The following procedures may be completed over multiple days, but within a 7-day window. Participants will be instructed to bring their HR monitor to the appointment and to refrain from exercise for 24 hours prior to cognitive testing, fMRI (for approved sites), and the LP. Cognitive testing should not be completed while participants are fasting, and if conducted after an LP, testing must be administered at least 48 hours following the procedure. Month 12 procedures include:

- Fasting blood collection for clinical labs
- Fasting blood collection for banking
- Medication review
- Brief physical exam, vital signs, weight
- Brief neurological exam
- AE query
- Briefly review adherence with participant using report provided through EDC and entries in the Physical Activity Logs (adherence will be regularly monitored by the YMCA Trainer, the Y-PM and the Intervention Oversight Team as well)
- Cognitive assessment
  - Primary outcomes assessment (administer the following tests before administering other cognitive/behavioral instruments)
    - ✓ ADAS-Cog13
    - ✓ Trail-Making Test
    - ✓ DSST
    - ✓ Category and Letter Word Fluency

- Secondary outcomes assessment
  - ✓ 3MSE/MMSE
  - ✓ iPad computer tests
    - Cogstate: DET, IDN, OCL, OBK, GMLT, FNAME, BPSO
    - NIH Toolbox: Flanker, DCCS
- Behavioral/functional and other outcomes assessments
  - Staff-administered questionnaires
    - ✓ CDR
    - ✓ ADCS-ADL-MCI
    - ✓ BRIEF-A
    - ✓ NPI
  - Self-administered questionnaires
    - ✓ By participant
      - Cognitive Change Index
      - SF-36
      - EQ5D
      - Research Satisfaction Survey
    - ✓ By study partner
      - Study Partner Self-Assessment Questionnaire (SF-36, Pittsburgh Sleep Quality Index, Insomnia Severity Index)
      - EQ5D (as it relates to participant)
- 400 m Walk Test
- Brain MRI
  - At approved sites, protocol will include fMRI sequences
- LP
  - CSF may be collected at this visit, even if not successfully collected at Baseline
  - Follow-up telephone call by staff within 24 hours to query AEs
- Dispense ActiGraph Link for actigraphy data collection
  - Place on the participant's non-dominant wrist to initiate recording period

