| Telephone Call to Participant by Clinic YMCA Liaison (query AEs, obtain medication updates)  |          |           | X        | X     | X               |       |
| Trainer-Supervised Exercise Sessions                                                         |          |           | X        | X     | X               |       |
| Trainer-Administered Rating of Perceived Exertion                                            |          |           | X        | X     | X               |       |
| Trainer-Administered AE Checklist                                                           |          |           | X        | X     | X               |       |
| Randomization                                                                                            |          |           | X        |       |                 |       |
| Treatment Blinding Questionnaire                                                                         |          |           |          |       | X               | X     |
| Provide Study Close-Out Materials                                                                        |          |           |          |       |                 | X     |

 Following Month 12 assessment, participants continue with their assigned exercise program but without supervision in Months 13-18

 The Study Partner Self-Assessment Questionnaire is comprised of the SF-36, the Pittsburgh Sleep Quality Index, the Insomnia Severity Index, the EQ5D, and questions about healthcare utilization

 Screening MRI to be conducted following site PI confirmation that participant has met all other inclusion/exclusion criteria; fMRI sequences added to protocol for approved sites

 To be completed for fasting participants who agree to LP at Baseline and Month 12

 Logs reviewed by Trainers weekly (in months 1-12), and by Clinic YMCA Liaison monthly when retrieved from YMCA (months 1-18) to identify potential adherence issues

 See Section 9.0 for visit-specific instructions

 Telephone call to be completed monthly (months 1-18)

 Supervision provided by study-certified YMCA Trainers, beginning after randomization through Month 12; data collected include type of exercise completed, exercise duration, HR, RPE, and other intervention-specific details (e.g., body parts stretched, treadmill speed and grade)

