11.1 Analysis of the Primary Outcome

To address the aim for the primary analysis (**Aim 1**), longitudinal scores from baseline through Month 12 will be analyzed using a mixed effects model for repeated measures (MMRM) to test differences in ADAS-Cog-Exec (composite) change scores between intervention groups in the mITT Population, with type I error level set at 0.05.

The MMRM model includes terms for time, intervention assignment, and baseline ADAS-Cog-Exec plus covariates that include site, ApoE4 carrier status, sex, and additional covariates meeting the criteria below. The primary test compares group changes from baseline to the mean score obtained across the Month 6 and Month 12 assessments. When Month 6 or Month 12 data are missing for a participant, the endpoint consists of the score obtained at the available assessment visit.

When an individual test score of the ADAS-Cog-Exec composite is missing or not administered and the examiner indicated it is missing “for cognitive reasons”, the worst possible score is assigned for that individual test prior to constructing the ADAS-Cog-Exec score.

Potential confounders (baseline Walk Test time, age, education, 3MSE baseline score, and use of cholinesterase inhibitors) will be included in efficacy analyses as covariates if the following two conditions are satisfied: (1) imbalance at baseline ($p < 0.1$) and, (2) association between the covariate and the response ($p < 0.15$). Safety data will be analyzed using exact contingency table methods by intervention group assignment.

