11.2.2.3 AD biomarkers in CSF (ab42/ab40, ab42/tau, ab42/p-tau) and blood (ab42/ab40)

No adjustment to type 1 error level ($\alpha = 0.05$) will be made for secondary analyses.

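### Month 12 CSF from participants with no baseline CSF cannot enter the SAP's main CSF analyses, and neither document says how a missing CSF baseline is handled

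*Protocol*

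**What the plan says.** **Collection.** Under the lumbar puncture item for Month 12, Protocol 9.5 states: "CSF may be collected at this visit, even if not successfully collected at Baseline". CSF has only two time points. Footnote 4 of the Appendix 1 schedule reads "To be completed for fasting participants who agree to LP at Baseline and Month 12", and the table in Protocol 12.2 shows the same two visits. Protocol 12.2.3 expects most participants to have both punctures and requires the baseline one before randomization.

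**Analysis in the Protocol.** For Aim 6, Section 5.4.2 says "CSF biomarkers of brain health and disease will be examined using a similar analytic strategy to that described for the analysis of the primary outcome" and adds: "Covariate adjustment, sensitivity analyses, and multiple imputation analyses will be carried out as specified under Aim 1". In Section 5.4.1, "The MMRM model will include terms for time, intervention, and baseline ADAS-Cog-Exec", among other terms. One listed sensitivity analysis there is an analysis of covariance with multiple imputation of missing data.

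**Analysis in the SAP.** Section 11.1 says: "The MMRM model includes terms for time, intervention assignment, and baseline ADAS-Cog-Exec plus covariates". Its test is on change from baseline. Section 11.2.2 sends the three CSF ratios (11.2.2.3) through a similar approach. Section 11.3 does the same for the ratios in the Pre-Pandemic Subset (11.3.1.3) and for the individual CSF markers (11.3.3). Section 11.1 has a rule for a missing Month 6 or Month 12 score but none for a missing baseline. Section 12 lists no multiple imputation.

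**The concern.** The Aim 1 model was written for ADAS-Cog-Exec, where a missing baseline should be rare: inclusion criterion 20 asks that participants can complete all baseline assessments, and these precede randomization. CSF is different. Lumbar puncture is done only in those who agree, and Protocol 9.5 expressly foresees baseline CSF that could not be obtained. The SAP borrows the model without a rule for this pattern of missing data.

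Two things are at stake. Some randomized CSF data would be left out of the main CSF comparisons although a standard model could use them. And with no rule stated, whether to drop, impute or jointly model the unpaired samples could be decided after the data are seen, with the Protocol and SAP pointing in different directions on imputation.

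**Working it through.** **No figure to reproduce.** The sample-size sections cover ADAS-Cog and, in the Protocol, hippocampal volume and entorhinal thinning. Neither document gives a sample size, SD or power for CSF.

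**Step 1: what the Aim 1 model does with CSF.** There is no Month 6 CSF, so the endpoint reduces to Month 12. With CSF in place of ADAS-Cog-Exec, each participant needs a baseline value, both to form the change and to fill the covariate. A participant with Month 12 CSF only has neither and contributes nothing to that model. The same holds in every population in which the SAP repeats it.

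**Step 2: what such a sample is worth if baseline is modelled jointly.** Assume baseline and Month 12 values are bivariate normal with unit variance, correlation ρ and a common baseline mean. Let each arm have n pairs and m Month 12-only samples.

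- Variance of the arm difference from pairs alone: 2(1 − ρ²)/n.
- Variance from Month 12-only samples alone: 2/m.
- Adding the information: n/[2(1 − ρ²)] + m/2 = n/[2(1 − ρ²)] × [1 + (m/n)(1 − ρ²)].

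With f = m/n, the proportional gain is **f(1 − ρ²)**. Both f and ρ are assumed:

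| f (Month 12-only ÷ pairs) | ρ = 0.5 (1 − ρ² = 0.75) | ρ = 0.7 (0.51) | ρ = 0.9 (0.19) |
|---|---|---|---|
| 0.05 | 3.8% | 2.6% | 0.95% |
| 0.10 | 7.5% | 5.1% | 1.9% |
| 0.20 | 15.0% | 10.2% | 3.8% |

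**Step 3: numerical check.** The generalized least squares variance was computed for 100 participants per arm, of whom 20 have Month 12 only, so f = 20/80 = 0.25. At ρ = 0.5 it falls from 0.01875 to 0.01579, a gain of 18.8%; the formula gives 0.25 × 0.75 = 18.75%. At ρ = 0.7 and 0.9 the computed gains are 12.7% and 4.7%, against 12.75% and 4.75% by formula.

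**Step 4: what this means for precision.** An information gain of 15% shortens the standard error by 1 − 1/√1.15 = 6.7%. A gain of 0.95% shortens it by 1 − 1/√1.0095 = 0.5%.

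**Step 5: baseline-only samples.** In the same model, adding 20 or 50 baseline-only samples per arm to 100 pairs gave a 0.0% gain at ρ of 0.5, 0.7 and 0.9. With equal numbers per arm they inform only the common baseline mean, not the arm difference.

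**The case against.** A reader might infer that Month 12-only samples add nothing to any planned CSF outcome, and so that the lumbar puncture, with its stated headache risk of about 5% (Protocol 4.2), serves no purpose. The documents do not support this. Protocol 5.4.2 plans multiple imputation for CSF, and a Month 12 value could carry information there, in principle about as much as in Step 2. CSF is also collected for banking and later biomarker work (Protocol 3.10, 12.2 and 12.2.3). Whether the puncture should be done is a clinical matter and is not judged here.

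Three further objections are fair:

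- The need for a CSF baseline is inferred. The model terms are written out only for ADAS-Cog-Exec, and a similar approach leaves room to adapt. This stands as a caveat, but a test of change from baseline needs a baseline on any ordinary reading.
- Few unpaired samples may arise, since most participants are expected to have both punctures. This stands too: the gain may be near the bottom of the range.
- A baseline-adjusted model and a constrained longitudinal model are both valid, so the choice is partly preference. That is true when pairs are complete. Here the Protocol permits unpaired Month 12 samples, and only one of the two uses them.

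The imputation argument does not close the gap. Protocol 5.4.1 does not say whether missing baselines are imputed, and the SAP does not carry the analysis forward.

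**Conclusion.** The point holds as a small, inexpensive improvement. Under the SAP as written, Month 12-only CSF does not enter the main secondary or exploratory CSF analyses, and no rule covers a missing CSF baseline. Modelling baseline jointly would add roughly 1–15% information on the arm difference, for f of 5–20% and ρ of 0.5–0.9. If the markers are very stable within person (ρ = 0.9), the gain is only about 1–4%.

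These figures rest on assumed f and ρ, approximate normality, equal numbers per arm, and unpaired samples missing at random given arm and the observed values. The pairs-only analysis is not assumption-free either: it needs a missing baseline to be unrelated to the Month 12 value, given arm and covariates.

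It would be too much to infer that every CSF sample would then contribute. Baseline-only samples would not add to the arm difference, although those participants can still serve the SAP 12.4 analyses of baseline CSF as a predictor of cognitive and imaging response. Month 12-only participants cannot enter those baseline-CSF subgroups under any of these models.

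**What to change.** In SAP 11.2.2.3, 11.3.1.3 and 11.3.3, specify a constrained longitudinal model for CSF:

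- baseline and Month 12 values both as responses;
- a common baseline mean across arms, which randomization after the baseline puncture justifies;
- unstructured covariance;
- the same site, ApoE4 and sex terms as in 11.1;
- the arm difference at Month 12 as the estimate.

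State in SAP Section 12 whether the Protocol's multiple imputation for CSF still applies and, if so, whether missing baselines are imputed. Report by arm the numbers with both samples, baseline only and Month 12 only. An analysis of pairs alone, under the Aim 1 model, can serve as the sensitivity analysis. If the Aim 1 model is kept as the main one, the SAP should say that Month 12-only samples are left out of it.

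The cost is SAP wording; the same kind of mixed-model software fits the model. The drawbacks are one model that differs from the Aim 1 template and reliance on missing at random for the unpaired samples.

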## 9.6 Month 18 (Visit 5)

The Month 18 assessment should be completed 18 months (+/- 2 weeks) from the participant's first appointment at the YMCA that initiated the intervention. Participants will be instructed to bring their HR monitor to the appointment and to refrain from exercise for 24 hours prior to cognitive testing, which should not be completed while fasting. Participants should also be asked to return all Physical Activity Logs for review and data entry, as this will be their final EXERT assessment. Month 18 procedures include:

- Fasting blood collection for clinical labs
- Fasting blood collection for banking
- Medication review
- Brief physical exam, vital signs, weight
- Brief neurological exam
- AE query
- Review returned Physical Activity Logs to ensure that they were completed and accurately reflect YMCA attendance records (provided in advance) and the participant's self-report
- Dispense ActiGraph Link for actigraphy data collection
  - Send device and instructions to participants 14 days before the Month 18 assessment; confirm with participant that the device was received and in place with a phone call at the start of the recording period
  - At the clinic visit, remove the device from the participant's wrist and upload data
- Cognitive assessment
  - Primary outcomes assessment (administer the following tests before administering other cognitive/behavioral instruments)
    - ✓ ADAS-Cog13
    - ✓ Trail-Making Test
    - ✓ DSST
    - ✓ Category and Letter Word Fluency
  - Secondary outcomes assessment (iPad computer tests)
    - ✓ Cogstate: DET, IDN, OCL, OBK, GMLT, FNAME, BPSO
    - ✓ NIH Toolbox: Flanker, DCCS
- Behavioral/functional and other outcomes assessment
  - Staff-administered questionnaires
    - ✓ CDR
    - ✓ ADCS-ADL-MCI
    - ✓ BRIEF-A
    - ✓ NPI
  - Self-administered questionnaires
    - ✓ By participant
      - Cognitive Change Index
      - SF-36
      - EQ5D

- Research Satisfaction Survey
- ✓ By study partner
  - Study Partner Self-Assessment Questionnaire (SF-36, Pittsburgh Sleep Quality Index, Insomnia Severity Index)
  - EQ5D (as it relates to participant)
- 400 m Walk Test
- Provide study close-out materials
  - Summary of progress in intervention
  - Fasting clinical blood test results from all visits
  - Color printout of single brain MRI image if available
  - Study completion certificate
  - 'Thank-you' gift or payment for participation
  - Participant's HR monitor (change battery)
  - Contact information for a YMCA staff member who will provide a personal coaching session at the YMCA, at no cost
- Site PI and Raters to complete Treatment Blinding Questionnaire

## 10.0 EARLY INTERVENTION DISCONTINUATION

Investigators at each site will make every effort to maximize participant retention. If a participant expresses a desire to stop the intervention, the Intervention Oversight Team will be notified and will hold a conference call with the Clinic YMCA Liaison and/or site investigator, and Y-PM and/or Trainer to discuss the participant's existing challenges and possible approaches to reduce burden to encourage continued participation if at all possible (e.g., adapt exercise routine to reduce pain or increase interest, problem-solve regarding transportation issues, etc.).

If a participant continues to decline further participation, or if an investigator discontinues the intervention, an Early Discontinuation Visit should be completed as soon as possible just prior to or immediately following intervention discontinuation. The Early Discontinuation Visit will include all Month 12 assessments to permit collection of primary and secondary outcome measures. If this Early Discontinuation Visit occurs before the start of Month 4, then the MRI and LP (when applicable) should not be completed. Alternatively, if an in-person Early Discontinuation Visit cannot be completed, site personnel should complete, by telephone, as many of the Month 12 procedures as possible (e.g., medication review, AE query, request return of Physical Activity Logs for review and data entry, CDR, Cognitive Change Index, SF-36, ADCS-ADL-MCI, BRIEF-A, NPI, Research Satisfaction Survey, EQ5D, Study Partner Self-Assessment Questionnaire).

All early intervention discontinuation participants will be strongly encouraged to complete not only the Early Discontinuation Visit, but also all regularly scheduled clinic assessments through Month 18.

